## 8.10 IMMUNOGENICITY ANALYSIS

Post-baseline cellular and humoral response magnitude will be summarized with medians and associated non-parametric 95% CIs. Post-baseline tissue response magnitude will be summarized with means and associated t-distribution based 95% CIs.

Valid samples for statistical analysis purposes will be those collected within 7 or 14 days of the specified time points (see [Table 1](#)). Baseline is defined as the last measurement prior to the first treatment administration.

### **8.11 SAFETY ANALYSES**

All AEs will be summarized among the safety population by frequency per treatment arm. These frequencies will be presented overall and separately by dose, and will depict overall, by system organ class and by preferred term, the percentage of subjects affected. Additional frequencies will be presented with respect to maximum severity and to strongest relationship to Study Treatment. Multiple occurrences of the same AE will be counted only once following a worst-case approach with respect to severity and relationship to Study Treatment. All serious AEs will also be summarized as above.

The main summary of safety data will be based on events occurring within 14 days of any dose. For this summary, the frequency of preferred term events will be summarized with percentages and exact Clopper-Pearson 95% confidence intervals. Separate summaries will be based on events occurring within 7 days of any dose and regardless of when they occurred.

Any AEs with a missing or partial onset date will be included in the overall AEs, but not be included within specified day-range summaries. AE duration will be calculated as (Stop Date – Start Date) + 1.

Measurements for vital signs as well as changes from baseline will be summarized with descriptive statistics: mean standard deviation, minimum, median, and maximum values by time point and treatment arm, for the mITT population. Baseline is defined as the last measurement prior to the first treatment administration.

The percentage of subjects with abnormal physical examination findings at each time point will be summarized by treatment study group and by body system, for the mITT population.

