### 3.1 TREATMENT REGIMENS

All eligible subjects who consent to participate in the study will receive four doses of 6 mg of VGX-3100 administered by IM injection followed by EP. The first dose will be administered as soon as possible following confirmation of the HSIL diagnosis, HPV-16/18 status and all other eligibility criteria but no more than 10 weeks following collection of the subject's biopsy specimen used for diagnosis by the PAC.

Each dose of VGX-3100 will be administered in a 1 mL volume IM (deltoid preferred site, or the anterolateral quadriceps as an alternate site) followed immediately by EP with the CELLECTRA™ 2000 device. [Figure 1 \(Appendix A\)](#) shows the original study visit schedule, in which study subjects will receive at least 4 doses of VGX-3100 and potentially a 5th and 6th dose depending upon their disposition with regard to histologic and lesion area changes. [Figure 1a](#) shows the revised visit schedule per Protocol Amendment 5.0. In both schedules, the first dose will be administered on Day 0, the second at Week 4, the third at Week 12, and the fourth dose will be administered at Week 24. Subjects with no HSIL at Week 48 (Subgroups A and B) will receive 4 doses. Subjects with HSIL at Week 48, who have a reduction in lesion size or no increase in lesion size from baseline (Subgroups C or D), may receive a fifth dose at Week 52 per the judgment of the Investigator.

With Amendment 5.0, subjects will complete the study at Week 78 and will not be offered a 6th dose. Subjects who were beyond Week 78 at the time of IRB approval of Amendment 5.0, will return for their final visit at their next scheduled timepoint as outlined in [Table 1](#). Subjects must sign the IRB-approved informed consent document for Amendment 5.0 prior to the initiation of procedures for their final study visit.

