Imiquimod treatment – Participants who have been enrolled in the VGX-3100 with imiquimod study group will continue with study visits per protocol, but no further participants will be enrolled into this study group. Subjects randomized to the VGX-3100 with imiquimod study group will apply imiquimod 5% cream to the vulvar lesion beginning in the evening on Day 0, and will continue to apply treatment three times per week for 20 weeks (inclusive of administration in the evening of VGX-3100 dosing). Subjects unable to tolerate imiquimod treatment may reduce their dosing frequency, and will document their use on the imiquimod dosing log provided.

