## 8.8 PRIOR AND CONCOMITANT MEDICATIONS

Prior medications are considered those medications taken prior to the first dose of study drug (i.e., Day 0). Concomitant medications are those used on or after Day 0. Partial start dates of prior and concomitant medications will be assumed to be the earliest possible date consistent with the partial date. Partial stop dates of prior and concomitant medications will be assumed to be the latest possible date consistent with the partial date. Data for all prior and concomitant medications will be summarized with percentages by treatment arm, for the mITT population.

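### The AE table that Section 8.11 labels main is incomplete by rule, and vital signs and physical findings are tabulated on the efficacy population

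*Protocol*

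**What the plan says.** The text at issue is Section 8.11 of protocol Version 5.0. It begins with the full AE tabulation: "All AEs will be summarized among the safety population by frequency per treatment arm". It then ranks the tables: "The main summary of safety data will be based on events occurring within 14 days of any dose". The sentence that follows gives this table percentages and exact Clopper-Pearson 95% intervals by preferred term. Two further tables are planned without any stated intervals: "Separate summaries will be based on events occurring within 7 days of any dose and regardless of when they occurred". The date rule is: "Any AEs with a missing or partial onset date will be included in the overall AEs, but not be included within specified day-range summaries".

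Vital signs are to be summarized with descriptive statistics up to "maximum values by time point and treatment arm, for the mITT population", and physical examination findings are assigned to the same population. Section 8.4 defines the mITT as dosed subjects who have the endpoint of interest, grouped as randomized, and makes it primary for efficacy. The same section defines a safety set of all dosed subjects, analysed by the treatment received.

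For exposure, Section 3.1 says that women in the combination group "will continue to apply treatment three times per week for 20 weeks" from Day 0. For VGX-3100, "the first dose will be administered on Day 0, the second at Week 4, the third at Week 12", with a fourth dose at Week 24 and an optional fifth at Week 52. For medications, Section 8.8 handles an incomplete start date differently: it "will be assumed to be the earliest possible date consistent with the partial date".

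**The concern.** Safety is secondary objective 1, and the table called main, the only one with stated intervals, is the one most likely to be reported and compared between groups. Three rules affect what the safety tables show.

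- An AE whose onset is known only to the month is removed from the main table even when that month is compatible with a post-dose window.
- The windows appear to follow the injections. Imiquimod is applied for 20 weeks, and Section 1.1.16 names local skin and application-site reactions as its most frequent adverse reactions.
- Two safety tables rest on a population built for efficacy, which may exclude dosed women and does not group them by what they received.

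All of this is written into the protocol, so it is not a detail left open for a later document.

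**Working it through.** The plan gives no figure of its own on this point, so there is nothing to reproduce first.

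**1. Share of imiquimod days inside the main window**

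Inputs: imiquimod for 20 weeks = 140 days, three times a week = 60 applications (Section 3.1); VGX-3100 on Days 0, 28, 84 and 168 (Section 3.1); window of 14 days (Section 8.11).

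If dose means a VGX-3100 dose:
- Windows within the imiquimod period: Days 0–13, 28–41 and 84–97. The Day 168 window starts after imiquimod ends on Day 140, and the optional Week 52 dose is later still.
- Coverage = 3 × 14 / 140 = 42/140 = 30.0%. Outside: 98/140 = 70.0%.
- Counting the dose day as an extra day: 3 × 15 / 140 = 45/140 = 32.1%.
- Moving doses 2 to 4 anywhere within their ±7-day visit windows leaves 42 days, because no windows overlap and the fourth still starts after Day 140.
- The 7-day summary covers 3 × 7 / 140 = 21/140 = 15.0%.

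If each imiquimod application also counts as a dose, coverage in the combination group is 140/140 = 100%. The VGX-3100-alone group stays at 42 of the same 140 days, so the two columns of the main table would cover different lengths of time.

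The summary without a time limit covers 100% on either reading.

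**2. Partial dates**

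| Item | Rule for an incomplete start date | Effect |
|---|---|---|
| Medications (Section 8.8) | earliest date compatible with the known part | always classified |
| AEs, overall table (Section 8.11) | retained | counted |
| AEs, 14-day and 7-day tables (Section 8.11) | excluded | not counted, even if the known part fits the window |

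The number of such AEs cannot be derived from the protocol. Partial dates are plausible after a fifth dose. Table 1 schedules no contact between Weeks 52 and 74, and the diary covers 7 days, so an event in the second week after that dose may first be recorded some 20 weeks later (74 − 54 = 20). That is an inference; the exclusion rule itself is explicit.

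**3. Population for vital signs and physical findings**

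Section 8.3 assumes 90% evaluable at Week 48, counted from randomization.
- If the endpoint that mITT requires is the Week 48 endpoint: 36 × (1 − 0.90) = 3.6 women omitted, made up of 24 × 0.10 = 2.4 and 12 × 0.10 = 1.2 by planned group.
- If it means the vital sign or examination being tabulated: no woman with a measurement is omitted. The only difference is grouping as randomized rather than as treated.

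**The case against.** The strongest reply is that no AE disappears. Section 8.11 tabulates all AEs on the safety population, keeps partly dated ones in the overall table and adds a table without a time limit. This stands. A reader might infer that the safety analysis as a whole undercounts AEs, and the text does not support that. The shortfall is confined to the 14-day and 7-day tables.

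Nor can the 30% be read as a share of events, or as showing that most application-site reactions are missed. The table counts women, each once per event term, so one onset in any window is enough, and the first two weeks of cream use lie inside a window. The documents say nothing about when onsets occur. The 30% also depends on what dose means. The synopsis ties the safety diary to VGX-3100 doses, and a breakdown of AEs by dose makes little sense for 60 applications, but the protocol also speaks of imiquimod doses and dosing. The term is undefined in Section 8.11.

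The contrast with Section 8.8 has limits. That rule sorts medications into prior and concomitant; applied literally to AEs, the earliest date could place an event before the dose that preceded it. Section 8.13 also says missing data are not imputed. But counting an event as compatible with a window requires no imputed date, and Section 8.8 already departs from that principle for dates.

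Finally, a reader might take the mITT choice as another route to fewer AEs. It is not. These are descriptive statistics and percentages whose denominator changes too, and AEs arising from examinations are tabulated on the safety set.

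**Conclusion.** The point holds within limits. The AE analysis is complete, but the table given main status and exact intervals is not. It excludes partly dated AEs by rule, by a number that cannot be estimated in advance. On the more natural reading of dose, it also observes 42 of 140 imiquimod days (30% of days). On the other reading it observes all of them in one group and not in the other, so the term needs defining either way.

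Using the mITT for vital signs and physical findings is a mismatch, since a suitable safety set is defined and is already used for AEs. Its size ranges from a difference in grouping alone to the omission of about 10% of women (3.6 of 36), depending on how the endpoint of interest is read and on the planned 90% evaluability being met.

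**What to change.** 1. In Section 8.11, summarize vital signs and physical findings on the safety analysis set, by treatment received.
2. Count an AE with a partial onset date in a day-range summary unless the known part of the date rules the window out. Report AEs with wholly missing onset dates as a separate sensitivity count, since otherwise one such event could enter every window. Add a matching exception to Section 8.13.
3. State that dose in the day-range summaries means a VGX-3100 dose. Give the existing summary without a time limit the same exact intervals and equal main status in both groups. A longer main window for the imiquimod group alone should be avoided, because it would make the main table non-comparable between groups.

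The cost is programming only, with no new data, visits or subjects. AE percentages in the day-range tables may rise slightly.

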### **8.12 PATIENT REPORTED OUTCOMES**

As an exploratory endpoint, patient reported outcomes will be summarized with medians or proportions of subjects with endpoints and associated non-parametric or exact Clopper-Pearson 95% CIs, for continuous responses and binary responses, respectively.

### **8.13 MISSING VALUES**

Missing data will not be imputed or replaced, and calculations will be done on reported values.

### **8.14 INTERIM ANALYSES**

No formal interim analyses will be performed for this study.

## **9. ETHICS**

### **9.1 INVESTIGATOR AND SPONSOR RESPONSIBILITIES**

The Investigator and Sponsor are responsible for ensuring that the clinical study is performed in accordance with the protocol, the Declaration of Helsinki, principles of Good Clinical Practice (GCP), and applicable regulatory requirements.

### **9.2 INSTITUTIONAL REVIEW BOARD OR ETHICS COMMITTEE (IRB/EC)**

The Investigator will undertake the study after full approval of the protocol and adjunctive materials (e.g., informed consent form, advertising) has been obtained from the applicable IRB/EC and a copy of this approval has been received by the sponsor.

Investigator responsibilities relevant to the IRB include the following:

- During the conduct of the study, submit progress reports to the IRB/EC as required.
- Notify the Sponsor immediately of any SAEs or serious unanticipated adverse device effects.
- If Sponsor notifies you about any reportable safety events notify the IRB immediately.
- As required, obtain approval from the IRB/EC for protocol amendments and for revisions to the consent form or subject recruitment advertisements;
- Reports on, and reviews of, the trial and its progress will be submitted to the IRB by the Investigator at intervals stipulated in their guidelines and in accordance with pertinent regulations and guidelines.
- Maintain a file of study-related information that includes all correspondence with the IRB;
- Notify IRB when study is completed (i.e. after the last study visit of the final study subject);
- After study completion provide the IRB with a final report on the study.

### **9.3 OFFICE OF BIOTECHNOLOGY ACTIVITIES (OBA)**

The Investigator and Sponsor are responsible for ensuring that the clinical study is reviewed and approved according to local and applicable global regulations (e.g., NIH Office of Biotechnology Activities) governing research that involves recombinant or synthetic nucleic acid molecules.

### **9.4 COMPLIANCE WITH INFORMED CONSENT REGULATIONS**

Written informed consent is to be obtained from each subject prior to Screening into the study, and/or from the subject's legally authorized representative. The process for obtaining informed consent must also be documented in the subject's medical record.

### **9.5 COMPLIANCE WITH IRB/EC REQUIREMENTS**

This study is to be conducted in accordance with applicable IRB/EC regulations. The Investigator must obtain approval from a properly constituted IRB/EC prior to initiating the study and re-approval or review at least annually. Sponsor is to be notified

immediately if the responsible IRB/EC has been disqualified or if proceedings leading to disqualification have begun. Copies of all IRB/EC correspondence with the Investigator must be provided to Sponsor.

## **9.6 COMPLIANCE WITH GOOD CLINICAL PRACTICE**

This protocol is to be conducted in accordance with the applicable GCP regulations and guidelines.

## **9.7 COMPLIANCE WITH ELECTRONIC RECORDS/SIGNATURES REGULATIONS (21CFR PART 11)**

When applicable, this study is to be conducted in compliance with the regulations on electronic records and electronic signature.

## **9.8 COMPLIANCE WITH PROTOCOL**

Subjects will be asked to complete a participant diary and, for subjects in the imiquimod study group, a dosing log during their study participation. Subjects will be provided with Investigator emergency contact information and advised to report all adverse events. While every effort should be made to avoid protocol deviations, should a deviation be discovered, the Sponsor must be informed immediately. Any protocol deviation impacting Subject safety must be reported to the Medical Monitor immediately.

## **9.9 CHANGES TO THE PROTOCOL**

The Investigator should not implement any deviation from or changes to the protocol without approval by the Sponsor and prior review and documented approval/favorable opinion from the IRB of a protocol amendment, except where necessary to eliminate immediate hazards to study subjects, or when the changes involve only logistical or administrative aspects of the study (e.g., change in monitors, change of telephone numbers).

# **10. DATA COLLECTION, MONITORING AND REPORTING**

## **10.1 CONFIDENTIALITY AND PRIVACY**

A report of the results of this study may be published or sent to the appropriate health authorities in any country in which the study products are legally marketed or may ultimately be marketed, but the subject's name will not be disclosed in these documents. The subject's name may be disclosed to the study sponsor, Sponsor, the governing health authorities or the Food and Drug Administration (FDA), if they inspect the study records. Appropriate precautions will be taken to maintain confidentiality of medical records and personal information.

Written Authorization and other documentation in accordance with the relevant country and local privacy requirements (where applicable) are to be obtained from each subject prior to enrollment into the study, and/or from the subject's legally authorized representative in accordance with the applicable privacy requirements (e.g., the Health Insurance Portability and Accountability Act Standards for Privacy of Individually Identifiable Health Information (HIPAA)).

Information about study subjects will be kept confidential and managed according to the requirements of the Health Insurance Portability and Accountability Act of 1996 (HIPAA). Those regulations require a signed subject authorization informing the subject of the following:

- What protected health information (PHI) will be collected from subjects in this study
- Who will have access to that information and why
- Who will use or disclose that information
- The rights of the research subject to revoke their authorization for use of their PHI

The rights of the research subject to revoke their authorization for use of their PHI.

## 10.2 SOURCE DOCUMENTS

Source data is all information, original records or clinical findings, laboratory results, observations, or other activities in a clinical trial necessary for the reconstruction and evaluation of the trial. Source data are contained in original source documents. Examples of these original documents, and data records include: hospital records, clinical and office charts, laboratory notes, memoranda, subject's diaries or evaluation checklists, pharmacy dispensing records, recorded data from automated instruments, copies or transcriptions certified after verification as being accurate and complete, microfiches, photographic negatives, microfilm or magnetic media, x-rays, subject files, and records kept at the pharmacy, at the laboratories, and at medical records and within information technology systems that are involved in the clinical trial.

A medical history must be present in the source documents. A medication history must be present in the source documents. All prescription and nonprescription medications taken within 1 week prior to entry must be recorded on the CRF. Actual or estimated start and stop dates must be provided.

## 10.3 RECORDS RETENTION

Upon request of the monitor, auditor, IRB/EC, or regulatory authority, the Investigator/institution should make available for direct access all requested trial related records.

CRFs will be provided for each subject. Subjects must not be identified by name on any CRFs. Subjects will be identified by their subject identification number (SID).

It is the Investigator's responsibility to retain study essential documents for at least 2 years after the last approval of a marketing application in an ICH region and until there are no pending or contemplated marketing applications in an ICH region or at least 2 years have elapsed since the formal discontinuation of clinical development of the investigational product. The sponsor will inform the Investigator/institution as to when these documents are no longer needed to be retained.

## 10.4 SAFETY AND QUALITY MONITORING

### 10.4.1 DATA & SAFETY MONITORING BOARD

A Data & Safety Monitoring Board (DSMB) will be established to protect the research subjects through independent analysis of emerging data from the trial. The DSMB will meet quarterly or as data are available to review safety data and regression/clearance results. If there are no new safety data or regression/clearance results to review for a quarterly scheduled meeting the DSMB will be notified and the meeting may be cancelled; Ad hoc meetings may be scheduled to review new data as applicable. The DSMB will be charged with advising the Sponsor if there appears to be a safety issue. No formal interim analysis will be performed. The DSMB Chair, upon consultation with the other voting members of the DSMB, has the authority to recommend suspension or stopping the study and to request a full DSMB review and ad hoc statistical analyses. The standard operating procedures of the DSMB will be documented in the DSMB charter, including the board's accountability to Inovio.

### 10.4.2 PATHOLOGY ADJUDICATION COMMITTEE

All vulvar biopsies will be read by a central expert PAC to ensure consistent assignment of disease status for both study eligibility and the efficacy analysis. The PAC will consist of up to four pathologists. Each specimen will be read by two pathologists independently in a masked fashion. The responsibilities and membership structure of the PAC is outlined in the PAC Charter, including the reporting of results.

### 10.4.3 CLINICAL MONITORING

Clinical Monitoring of the trial will be performed by experienced monitors, who will report to the Sponsor or the Sponsor designee. Records for all clinical subjects in this trial will be monitored. The following clinical site monitoring tasks will be performed at all sites:

- Prior to trial initiation, a site visit will be conducted to review all relevant forms and documentation, to ensure the site is qualified and compliant with all applicable requirements.
- All clinical site monitoring visits will be documented.
- Periodic site visits will be performed throughout the study.
- The site monitor will be responsible for addressing and documenting the following study conduct activities and obligations and will:
  - Assure that the study is being conducted in accordance with the protocol, applicable regulatory agency regulations, and IRB policies
  - Discuss study conduct issues and incidents of noncompliance with the Investigator and/or study personnel and document them on the resolution trip report. Report any significant unresolved problems immediately to the sponsor.
  - Remind the Investigator as necessary of the obligation to immediately report all serious adverse events (SAE) and provide subsequent follow-up report of the final outcome to the IRB
  - Throughout the study, inspect all source documents to ensure they are complete, logical, consistent, attributable, legible, contemporaneous, original, and accurate (ALCOAC).
  - Assure that the study facilities continue to be acceptable

- Compare the study CRFs with source documents to assure that the data are accurate and complete and that the protocol is being followed
- Assure that investigational drug and device accountability and reconciliation of records are complete and accurate
- Assure that all subject specimens are being stored and forwarded properly for testing per laboratory manual requirements

